10.8.2 Laboratory Values

Clinical laboratory results post-Baseline will be evaluated for markedly abnormal values. For the incidence of markedly abnormal laboratory values, each patient may be counted once in the laboratory parameter value high and in the laboratory parameter low

categories as applicable. Descriptive summary statistics (e.g. mean, SD, median, minimum, maximum) for laboratory values and changes from baseline will be evaluated.

10.8.3 Vital Signs

Vital sign values will be evaluated on an individual basis by patient. Abnormal vital sign values will be identified as those outside (above or below) the reference range. Descriptive summary statistics (e.g., mean, SD, median, minimum, maximum) for vital sign parameters and changes from Baseline will be evaluated.

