4.4.1 Criteria for Stopping VentaProst Treatment

Individual patients stopping criteria: At any time during study drug administration, patients may be removed from study treatment and placed on standard of care (SoC) therapy if they meet one or more of the following pre-defined criteria leading to a deterioration in their condition:

- Severe hypotension as evidenced by a systolic BP < 90 mmHg or MAP < 60 mmHG for >2 hours from the start of VentaProst
- Need for VV ECMO
- Need to increase existing vasopressor therapy by more than 25%
- Worsening oxygenation, ventilatory, or hemodynamic parameters that in the opinion of the investigator the patient should be removed from study treatment
- Massive hemoptysis thought to be clinically significant and not due to endotracheal tube trauma
- Pulmonary Edema

Study stopping criteria: If 3 patients are removed from the study for any of the above conditions, the study will stop further enrollment and investigation will be conducted to determine the cause of the events. An independent safety evaluation will also be conducted. If it is suspected that the investigational product has caused the events, the study will be terminated.

Independent Safety Evaluation: Independent safety evaluation will be conducted by a licensed physician who is not involved in the VentaProst COVID-19 clinical study or the sponsoring organization.

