10.8 Safety Analyses

Safety measurements include AE/SAEs, vital signs, chest assessments (Chest CT or Chest X-ray), laboratory tests, and oxygenation/ventilatory parameters. Safety data will be summarized by using frequencies and incidence rates.

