10.8.1 Adverse Events

AEs will be classified into standardized medical terminology from the verbatim description (Investigator term) using the Medical Dictionary for Regulatory Activities (MedDRA). AEs will be presented by preferred term nested within System Organ Class. Verbatim description and all MedDRA level terms, including the lower level terms, for all AEs will be contained in the data listings of the clinical study report (CSR).

AEs will be summarized by presenting the incidence of AEs. Although a MedDRA term may be reported more than once for a patient, that patient will be counted only one time in the incidence count for that MedDRA term.

Treatment-emergent adverse events (TEAEs) will be analyzed. AEs that are not treatment-emergent will be listed. A TEAE is defined as

- AEs that emerge during treatment, having been absent at pretreatment, or
- Reemerge during treatment, having been present at pretreatment but stopped prior to treatment, or
- Worsen in severity or frequency during treatment relative to the pretreatment state, when the AE is continuous.

Adverse events of special interest (AESI) will be analyzed. An AESI is defined as:

- Serious or non-serious adverse that is one of scientific and medical concern specific to the sponsor's product for which ongoing monitoring and rapid communication by the investigator to the sponsor is required
- Events or symptoms thought to potentially be associated with the investigational compound, device, or disease under study, or
- Can arise with any use of a drug/device (e.g. off-label use, use in combination with another approved drug), with any route of administration, formulation, or dose, including an overdose.

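### The abnormality flags in Sections 10.8.2 and 10.8.3 are not conditioned on the baseline value, so patients already abnormal at entry can be flagged and new abnormality by arm is hard to read

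*Combined protocol and SAP*

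**What the plan says.** All references are to the current protocol version, the last in the combined file.

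- **Laboratory values (10.8.2).** "Clinical laboratory results post-Baseline will be evaluated for markedly abnormal values". For the incidence count, "each patient may be counted once in the laboratory parameter value high and in the laboratory parameter low" categories, so direction is kept apart. No limit for markedly abnormal is given, and no condition on the baseline result.
- **Vital signs (10.8.3).** "Abnormal vital sign values will be identified as those outside (above or below) the reference range". Values are reviewed patient by patient. No reference range is given, the flag is not restricted to readings after the first dose, and separate reporting of high and low is not stated.
- **Baseline comparison.** Both sections also plan descriptive statistics, including minimum and maximum: "for laboratory values and changes from baseline will be evaluated" (10.8.2) and "for vital sign parameters and changes from Baseline will be evaluated" (10.8.3).
- **Form of summary (10.8).** "Safety data will be summarized by using frequencies and incidence rates".
- **Adverse events (10.8.1).** The treatment-emergent definition is tied to the pretreatment state. Its first limb is "AEs that emerge during treatment, having been absent at pretreatment, or", followed by limbs for events that return or worsen.

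Section 10.1 says that no statistical analysis plan will be written, so no later document is due to settle these tables.

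**The concern.** Every patient enters on invasive ventilation for COVID-19, so some will probably have vital signs or laboratory values outside normal limits before the first dose. A flag that ignores the baseline value can count such a patient as abnormal whatever the drug does. This raises the flagged rate in both arms. With 10 patients per arm, a chance difference in how many enter abnormal also passes straight into the comparison.

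Section 2.2.5 names low blood pressure as a risk of the product. A table of pressures outside the range would not say how many patients in each arm moved from normal to low, which is the figure a reader of a small exploratory safety data set would look for.

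**Working it through.** **No figure to reproduce.** The documents give no flag rate, no share abnormal at entry and no sample-size calculation. The arithmetic below is illustrative, and all its rates are assumptions.

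**Inputs from the documents:** 10 patients per arm (3.3); 1:1 allocation (10.4); vital signs twice daily on Days 1-10 (7.1.1), so up to 20 scheduled readings.

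**Assumed inputs:** b = share abnormal at entry who are flagged later; p = rate of new abnormality among the rest, 10% on control and 40% on active; independent patients. Worsening from an abnormal baseline is left out for simplicity.

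**Formulas**

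- Flag as written: b + (1 − b)p.
- Treatment-emergent count over all treated patients: (1 − b)p.
- Expected difference between arms under either rule: (1 − b)(0.40 − 0.10).
- Standard deviation (SD) of the observed difference: √{[r₁(1 − r₁) + r₂(1 − r₂)]/10}, where r₁ and r₂ are the two arm rates.

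| b | Flag as written | Emergent, all treated | Difference (points) | SD, flag (points) | SD, emergent (points) |
|---|---|---|---|---|---|
| 0% | 10% vs 40% | 10% vs 40% | 30 | 18 | 18 |
| 20% | 28% vs 52% | 8% vs 32% | 24 | 21 | 17 |
| 40% | 46% vs 64% | 6% vs 24% | 18 | 22 | 15 |
| 60% | 64% vs 76% | 4% vs 16% | 12 | 20 | 13 |
| 80% | 82% vs 88% | 2% vs 8% | 6 | 16 | 10 |

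**Reading the table at b = 40%**

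1. The flag gives 4.6 against 6.4 patients of 10. The emergent count gives 0.6 against 2.4. Both differ by 1.8 patients, so the emergent count does not enlarge the difference. It removes the 4 patients per arm who were abnormal already.
2. The number abnormal at entry varies by chance. The SD of its difference between arms is √(2 × 10 × 0.4 × 0.6) = 2.2 patients, more than the 1.8 patients attributed to the drug. The flag carries that noise. The emergent count mostly does not, and its SD falls from 22 to 15 points.
3. Dividing by the 6 patients at risk would show 10% against 40%, a 30-point contrast. That larger figure comes from the denominator alone: the patients counted are the same 0.6 and 2.4.

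**Power.** With b = 0 and 10 per arm, 10% against 40% has 33% power by the normal approximation and 15% by Fisher's exact test (two-sided 0.05). At b = 40% Fisher power is about 4% under either rule (4.5% as written, 3.7% emergent over all treated).

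**Repeated readings.** If each of 20 readings had an independent 5% chance of being out of range (assumed), 1 − 0.95²⁰ = 64% of patients would have at least one flag on that parameter. Conditioning on baseline does not remove this, because any worst-value summary shares it.

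**The case against.** The case against is substantial, and much of it stands.

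- **Baseline is not ignored.** A reader might infer that these sections make no use of baseline. They do: both evaluate changes from baseline with minimum and maximum, so the largest individual fall in pressure will appear. Section 10.8.3 reviews vital signs by patient and Section 10.3 promises individual listings, which about 20 patients make workable.
- **Hypotension is not hidden.** A reader might infer that it would be buried. It can also surface as an adverse event if it needs intervention or changes treatment (7.2.6), through the new-or-worse rule (10.8.1), through the haemodynamic and vasopressor components of the primary endpoint (10.6.1), and through the stopping criterion in 4.4.1. Exclusion 9 keeps out patients judged haemodynamically unstable. Nor do the documents rank hypotension as the main expected harm: 2.2.5 names it, but special-interest status in 7.2.2 goes to pulmonary oedema and pulmonary haemorrhage.
- **Pooling is not stated.** A reader might infer from the words on direction in 10.8.3 that a fever and a pressure fall count alike. The text does not combine directions or parameters. It is silent on separate reporting, whereas 10.8.2 is explicit.
- **An incidence count is set only for laboratory values.** Section 10.8.3 identifies abnormal vital signs. A count follows only through the general sentence in 10.8. The laboratory flag also requires a marked abnormality, which fewer patients may show at entry.

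What survives is that none of these routes gives, by arm, the number of patients who moved from normal to abnormal or from abnormal to worse. A minimum change shows one patient, a listing is not a count, an adverse event depends on investigator judgement or clinical action, and removal under 4.4.1 is discretionary with no planned table by arm.

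**Conclusion.** The point holds as a gap in table specification. The two flags are not conditioned on baseline, and the vital-sign flag is not confined to post-baseline readings, although 10.8.1 applies a new-or-worse rule to adverse events and the baselines are collected (Screening for laboratory tests in 7.1.3; Screening and 0 Hr for vital signs in Table 2). The result is a raised rate in both arms, extra noise from chance imbalance, and a less legible picture of new abnormality, including low blood pressure.

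The size cannot be taken from the documents. Under the assumed rates with 40% abnormal at entry, 46% against 64% becomes 6% against 24%, with the same 18-point difference and about 7 points less standard deviation. A smaller share abnormal at entry makes the point smaller, and at zero it vanishes. A reader might infer that the correction recovers a 30-point contrast or gives the trial power to detect harm. Neither follows: the first rests on a changed denominator, and power stays low. The gain is in interpretation.

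**What to change.** In Sections 10.8.2 and 10.8.3:

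1. Count treatment-emergent abnormality: normal at baseline and abnormal later, or worse than an abnormal baseline. State the baseline reading used, the reference ranges and the limits for markedly abnormal.
2. Report high and low vital signs separately for each parameter, as 10.8.2 already does for laboratory values.
3. Show baseline-to-worst shift tables by arm, including low blood pressure. Use all treated patients as the denominator and show the number at risk beside it.
4. If the pressure levels in 4.4.1 are borrowed ("Severe hypotension as evidenced by a systolic BP < 90 mmHg or MAP < 60 mmHG"), label them a reporting threshold on scheduled readings without the duration of more than 2 hours, since twice-daily readings cannot establish it. Show baseline status alongside. Leave the stopping rule unchanged.
5. Label any percentage-point illustration as assumed.

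The cost is slightly more table programming. The needed values are already scheduled: systolic and diastolic pressure are recorded under 7.1.1, and mean pressure can be derived from them. The drawback is that at-risk numbers will be small, and the tables should be read as description rather than as a test.

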2.2.5 Summary of Known and Potential Risks of Inhaled Epoprostenol Administration

Safety of inhaled epoprostenol in cardiothoracic surgery patients is remarkable. In the reported literature to date, there were no reports of serious or life-threatening drug-related safety events. Due to its mechanism of action, inhaled epoprostenol may theoretically cause increased bleeding (anti-platelet mechanism) or systemic vasodilation consequent to spill over into the central circulatory system, but no such events have been reported. Some accounts of the use of inhaled prostacyclin in the chronic setting (e.g. iloprost for PAH) report transient events as listed on the approved product labeling. These include cough, headache, flushing, and an influenza-like syndrome. However, these types of events are unlikely to be reported due to sedation in the ICU setting.

VentaProst may result in hypotension, which will be monitored via frequent - assessments of oxygenation, ventilatory and hemodynamic parameters and vital signs. Pulmonary edema and pulmonary bleeding are potential risks due to the drug's mode of action (refer to Section 7.2.2). Worsening oxygenation is a theoretic concern through worsened ventilation/ perfusion matching. This will be monitored through continuous pulse oximetry throughout the administration of the inhaled epoprostenol.

Risks to subjects in this study are related to common procedures performed (e.g., venipuncture) and the documented adverse events (AEs) listed in the current Investigator's Brochure. These risks are communicated to the subjects in the consent forms. There may be additional risks that are currently unknown.

The benefits of the study may include targeted lung vasodilation and improved oxygenation, potential anti-platelet effects on the lung vasculature, reduction in disease progression, avoidance of greater oxygen needs and early weaning off mechanical ventilation. If the drug does have such properties, then this may aid recovery, improve outcomes and enable an earlier discharge from the hospital.

There is no funding awarded to the patients participating in this study.

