7.1 General Safety Procedures

7.1.1 Vital Signs and Weight Measurements

Vital sign measurements, including systolic blood pressure (SBP), diastolic blood pressure (DBP), heart rate (HR) [beats per minute], respiratory rate (breaths per minute), and body temperature (in Celsius) will be obtained twice daily Days 1-10 or as clinically indicated. Weight (kg) will be obtained at the time of Screening and at Day 10 or end of VP treatment. Height will be obtained at the time of Screening. If unable to obtain height, the study staff will use the best reported historical height from patient or LAR.

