9.1.2.4 Days 2-10 (While on study drug)

- Continue to administer study drug if clinically indicated.
- Adverse Event/SAE assessment daily
- Concomitant medication evaluation daily
- Oxygenation measurement via continuous pulse oximetry (SpO₂)
- Ventilatory parameters assessed twice daily: Ventilator Type, Vent Mode, FiO₂, Inspiratory time, Mean Airway Pressure, Peak Inspiratory Pressure, Positive End Expiratory Pressure, Tidal Volume, and Respiratory Rate
- Vital signs will be assessed twice daily in AM and PM. Efforts will be made to obtain vital signs at the same time each day. Vital signs include: temperature, pulse rate, and blood pressure.
- Time Prone Position-16 hours per day per OSU Protocol

- Chest X-ray (Days 3-8 as clinically indicated)
- Full Chemistry Panel including LFTs, CBC with Diff including neutrophils and lymphocytes, PT/PTT, troponin, and BNP(Days 5 & 10).
- Triglycerides, LDH, ferritin, fibrinogen, CRP, ESR, IL 6 and D-Dimer may be collected if the subject's condition warrants it at Days 5 and Day 10.
- Obtain weight. (Day 10 only or at end of study drug dosing)

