10.6 Criteria for Evaluation

10.6.1 Primary Efficacy Endpoint

The primary efficacy endpoint:

- 1. Reduction of respiratory failure. Failure is defined by any one of the following:
 - Requires VV ECMO
 - Inability to extubate patient within 10 days or reintubation within <24 hours
 - Change in S/F, oxygenation index and P/F ratio (\geq 15%) from baseline to 12 hours, Days 1, 2, 3, 4, 5, 6, 7, 8, 9 and Day 10 (or end of treatment)

or

- 2. Reduction of cardiac or circulatory failure. Failure is defined by any one of the following:
 - Need to begin inotropic therapy or 10% increase in current vasopressor therapy

- Worsening hemodynamic parameters
- Cardiac troponin >20 % from baseline
- BNP \geq 15% of baseline
- Need for temporary mechanical circulatory support (IABP, Impella)
- Requires VA ECMO

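### Section 10.8.3 summarises blood pressure without regard to vasopressor support, so a fall corrected with a vasopressor is attenuated in that table

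*Combined protocol and SAP*

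**What the plan says.** All references are to the last (current) version of the protocol in the combined file. Section 10.1 says that no separate statistical analysis plan will be written.

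- **The risk.** Section 2.2.5 gives a mechanism, "systemic vasodilation consequent to spill over into the central circulatory system", and states "VentaProst may result in hypotension, which will be monitored via frequent" checks of oxygenation, ventilation, hemodynamics and vital signs. Hypotension is the first risk there for which monitoring is described.
- **The measurement.** Under Section 7.1.1, vital signs, including systolic and diastolic pressure, "will be obtained twice daily Days 1-10 or as clinically indicated".
- **The analysis.** Section 10.8.3 plans review patient by patient, then a flag: "Abnormal vital sign values will be identified as those outside (above or below) the reference range". It closes with the summary statistics: "Descriptive summary statistics (e.g., mean, SD, median, minimum, maximum) for vital sign parameters and changes from Baseline will be evaluated". Section 10.3 adds individual patient listings.
- **The support data.** Sections 9.1.2.2 to 9.1.2.4 list "Concomitant medication evaluation daily". Section 10 plans no table from these records.
- **Where vasopressors do appear.** The circulatory part of the primary endpoint (Section 10.6.1) includes "Need to begin inotropic therapy or 10% increase in current vasopressor therapy". Section 4.4.1 allows a patient to be taken off study treatment when existing vasopressor therapy must rise by more than 25%.

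**The concern.** The protocol itself expects vasopressor treatment to change during the study. In a ventilated patient, a recorded blood pressure reflects both the patient's circulation and the support being given. If the active drug lowers systemic pressure and the team starts or raises a vasopressor, the next reading is partly or fully restored. Both outputs of Section 10.8.3 then shrink: the mean change from Baseline and the count of readings below range. The difference between arms moves into the medication record, which Section 10 does not tabulate.

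The distortion has a direction. It makes a vasodilator look more neutral on blood pressure than it is, in the table where a reader would look first for this risk.

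**Working it through.** The plan gives no blood-pressure effect, SD or power to reproduce; the synopsis says no formal sample-size estimate was made. The check is therefore a comparison of sections plus an illustration.

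**1. Does any planned analysis show vasopressor use by arm?**

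| Route | What it captures | What it leaves out |
|---|---|---|
| 10.8.3 vital signs | Values, change from Baseline, out-of-range flags | Any reference to support |
| 10.6.1 primary endpoint | Starting an inotrope, or a 10% rise in a vasopressor already running | A first vasopressor start is not clearly covered. It is one of six circulatory items beside three respiratory ones, and the synopsis summarises success or failure, so the component need not be visible |
| 4.4.1 stopping criteria | A rise above 25% in existing therapy; sustained low pressure | Patient-level removal rules, not a comparison of arms. The pressure criterion uses recorded pressure alone |
| 7.2.6, 5.6 and 10.8.1 adverse events | An abnormality needing intervention should be reported, then tabulated by incidence | Depends on investigator reporting. 7.2.6 asks for a repeat test first, which may be normal once support is running. 7.2.2 does not list hypotension as an event of special interest |

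No route is planned as a by-arm display of vasopressor use.

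**2. Size of the attenuation.** All inputs are assumptions; none comes from the documents, and 65 mmHg is not proposed as a target.

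- Baseline mean arterial pressure has mean 75 and SD 8. Follow-up noise has SD 8. Support holds pressure at exactly c = 65.
- SD of unsupported follow-up pressure: s = √(8² + 8²) = 11.31.
- With unsupported mean μ and d = (μ − c)/s, the expected recorded pressure is c + s[φ(d) + dΦ(d)], and the share needing support is Φ(−d).

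| Arm | μ | d | Recorded mean | Needing support |
|---|---|---|---|---|
| Control | 75 | 0.884 | 76.17 | 18.8% |
| Active, 5 mmHg fall | 70 | 0.442 | 72.45 | 32.9% |
| Active, 10 mmHg fall | 65 | 0 | 69.51 | 50.0% |

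A true 10 mmHg fall appears as 76.17 − 69.51 = 6.7 mmHg, and a true 5 mmHg fall as 76.17 − 72.45 = 3.7 mmHg. Under this model nobody is recorded below 60 mmHg in either arm, but the floor builds that in; it is not a finding.

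**3. Precision with 10 per arm.** The 95% CI half-width for a mean difference is t(0.975, 18) × SD × √(2/10), with t = 2.101.

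- SD 7 (about the SD of change in the model above): 6.6 mmHg
- SD 10: 9.4 mmHg
- SD 15: 14.1 mmHg

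The approximate chance that the interval excludes zero in the right direction is Φ(Δ/(SD√0.2) − 1.96). For a true 10 mmHg fall of which vasopressors restore a given share:

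| Share restored | Δ seen | SD 10 | SD 15 |
|---|---|---|---|
| 0% | 10 | 61% | 32% |
| 50% | 5 | 20% | 11% |
| 75% | 2.5 | 8% | 6% |
| 100% | 0 | 2.5% | 2.5% |

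**4. Precision of the proposed display.** With true shares of 19% and 50% and 10 per arm, the power of Fisher's exact test is about 14%. A result of 2/10 against 5/10 gives p = 0.35.

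**The case against.** A reader might infer that no safety analysis touches the vasopressor record and that the trial would report no hypotension. The documents do not support that. Section 7.2.6 asks for a vital-sign abnormality that needs medical intervention to be reported as an adverse event. Section 5.6 has the investigator record adverse events for which a medication was given. Section 10.8.1 tabulates the incidence. Vasopressor escalation also counts toward the primary endpoint and the stopping criteria, and three removals pause enrolment. With about 20 patients, individual review and listings are practical.

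It would also be too strong to say that the fall shows as little or no change: under the stated model about two thirds of it remains. Nor is masking the only problem. At SD 15, even an unmasked 10 mmHg fall lies inside the 14.1 mmHg half-width. The added table is no more powerful as a test, and the documents do not confirm that vasopressor doses are recorded at times that match the pressure readings.

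All of this stands, and it limits the claim to the vital-sign table. It does not remove the bias there. A larger sample would narrow the interval around an attenuated difference without correcting it, and the other routes leave the gaps listed above.

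**Conclusion.** The point holds for Section 10.8.3. Its blood-pressure summaries are biased toward no difference between arms whenever vasopressors correct a drug-induced fall, and no planned table shows vasopressor use by arm. In the illustration, about a third of a 10 mmHg fall disappears (10 seen as 6.7), while the share needing support goes from about 19% to 50%. Those figures rest on the assumed baseline, noise and support level; the direction needs only that vasopressors raise pressure and are used more in the arm with the larger fall.

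The point does not extend to saying that the trial ignores vasopressors or would miss hypotension altogether. This is a worthwhile improvement to a descriptive safety analysis in an exploratory study. Since no separate analysis plan is to follow, Section 10.8.3 is the place to make it.

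**What to change.** Add one descriptive by-arm table to Section 10.8.3. For each day, give the number and percentage of patients with either:

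- blood pressure below the reference range that Section 10.8.3 already uses, or
- a vasopressor started or increased since Baseline.

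Show the two parts separately as well as combined. Take vasopressor starts and increases from the daily concomitant-medication records. Show vasopressor dose beside blood pressure only where dose is recorded. Keep the existing vital-sign summaries, flags and listings.

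The cost is a few sentences of analysis wording and one extra table. Before finalising it, confirm that the data collection forms identify vasopressor starts and increases by day. The table is for display, not testing: with about 10 patients per arm it will be imprecise. No dose, stopping rule or clinical management changes.
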